766 to contact study staff for a replacement of the meter, test strips, and control solution if a meter
767 fails QC testing at home.

768 Subjects will be instructed to perform blood ketone testing per the Glycemic Treatment
769 Guidelines located in the study training manual.

770 **4.2. Ecological Momentary Assessment Training**

771 After randomization, all participants will be trained on how to access and complete EMAs from
772 their study phone, how to postpone alerts, and enter a voluntary diary. Participants will be
773 informed when the EMAs are scheduled during each phase of the trial.

774 **4.3. Glucagon Emergency Kit**

775 A home glucagon emergency kit will be required. Participants who currently do not have one will
776 be given a prescription for the glucagon emergency kit.

777 **Chapter 5 Study Procedures**

778 **5.1. Study Contacts**

779 **5.1.1. Study Support**

780 Participants will also receive study staff contact information to ask any questions they may have
781 during the study. Additionally, participants will be provided with study contact information for
782 technical support with DiAs System, the study insulin pump and the study CGM. The participant
783 will be asked to call the study team at any time during the study for any health-related issues
784 (adverse events), including hypoglycemia <54 mg/dL, frequent highs >300 mg/dL, or ketones ≥3.0
785 mmol/L. The participant may use the study pump and study CGM during periods of DiAs
786 disconnections or technical difficulties.

787 **5.1.2. Web Conferencing**

788 Study visits may be completed using HIPAA compliant web conference tool. The study team will
789 provide the participant with the meeting information in advance of the appointment.

790 **5.2. Sensor-Augmented Mode (SAM) Run-in Period**

791 **5.2.1. CGM use**

792 Once all training activities are completed, the participant will be given adequate supplies to
793 complete the Run-in home use of the DiAs system in SAM.

794 Participants will complete a minimum of 14 days (if CGM use within the preceding 3 months) or
795 4 weeks (if no CGM use within the preceding 3 months) of home use of the DiAs system in SAM.
796 The study physician may request an additional run-in period of 2 weeks.

797 The participant will be informed that in order to be eligible for the study, the DiAs system in SAM
798 must be used on a minimum of 11 out of 14 days for CGM users or 22 out of 28 days CGM
799 nonusers.

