836 Once all training activities are completed, the participant will be given adequate supplies and
837 study devices to last until the subsequent clinic visit. An appointment for Visit 4 will be scheduled

838 **6.3. Home Use of DiAs in Phase 1 Mode**

839 The participant will complete a minimum of 8 weeks of DiAs use in Phase 1 Mode at home. During
840 the course of Phase 1, participants will complete EMA surveys and post-phase questionnaires.

841 **6.3.1. Phase 1 EMA Surveys**

842 Over the course of 2-3 days every two weeks of Phase 1, the participant will be asked to complete
843 a “Daily Diary” with 3-5 entries of 3-4 questions each day, for a minimum total of 48 entries per
844 participant during each Phase.

845 **6.3.2. Post-Phase 1 Questionnaires Week 7**

846 Participants randomized to escalation will be sent the following questionnaires on week 7 (day
847 42 of Phase 1) and will be asked to complete them within 1 week:

- 848 • Pittsburgh Sleep Quality Index

CLINICAL PROTOCOL

- 849
- Hyperglycemia Avoidance Scale

850 **6.3.3. Post-Phase 1 Questionnaires Week 8**

851 Participants randomized to escalation will sent the following questionnaires on week 8 (day 49
852 of Phase 1) and will be asked to complete them within 1 week:

- 853
- Confidence in Diabetes Self-Care Scale
- 854
- T1-Diabetes Distress Scale
- 855
- Hypoglycemia Fear Survey

856 **6.4. Visit 4 – Phase 2 Initiation**

857 All participants in each randomization scheme use PF in Phase 2. Phase 2 initiation may be
858 conducted either via web conference or an office visit. The participant will remotely receive a
859 mode change for Phase 2. Study staff will review the features of the Personalized Feedback (PF)
860 mode and answer any questions. Participant will have a blood/urine pregnancy test that must be
861 negative in order to continue to participate in this study.

862 **6.4.1. Training on Phase 2 DiAs Mode**

863 The participant will be trained on the following features of the Personalized Feedback System:

- 864
- **Tracking of estimated HbA1c:** When properly calibrated, eA1c is within 0.3% of
865 reference HbA1c on average, and within 1% of HbA1c >95% of the time.
- 866
- **Hypoglycemia Risk Indicator:** Provides an indication of the current risk for
867 hypoglycemia.
- 868
- **Insulin Sensitivity Profile & Indicator:** Tracks changes in insulin sensitivity (SI) and
869 creates daily and monthly SI profiles.
- 870

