1620 **Chapter 13 Miscellaneous Considerations**

1621 **13.1. Prohibited Medications, Treatments, and Procedures**

1622 Participants using glulisine at the time of enrollment will be asked to contact their personal
1623 physician to change their prescribed personal insulin to lispro or aspart for the duration of the
1624 trial.

1625 The study devices (study insulin pump, study CGM) must be removed before Magnetic Resonance
1626 Imaging (MRI), Computed Tomography (CT) or diathermy treatment. Participants may continue
1627 in the trial after temporarily discontinuing use if requiring one of the treatments above.

1628 **13.2. Participant Withdrawal**

1629 Participation in the study is voluntary. Participant may withdraw at any time. For participants
1630 who do withdraw from the study, the study team will determine if their data will be used in
1631 analysis.

1632 **13.3. Confidentiality**

1633 For security and confidentiality purposes, subjects will be assigned an identifier that will be used
1634 instead of their name. Protected health information gathered for this study may be shared with
1635 the third-party collaborators. De-identified subject information may also be provided to
1636 collaborators involved in the study after the appropriate research agreement has been executed.

1637 **Chapter 14 Statistical Consideration**

1638 **14.1. Design and Randomization**

1639 This is a randomized crossover study in T1DM designed to demonstrate the efficacy of
1640 personalized feedback (PF) and decision support (DSS) over sensor-augmented pump (SAM)
1641 therapy and to establish relationships between the level of glucose variability (GV) control
1642 achievable by the intervention and individual psycho-behavioral characteristics.

1643 We plan to split the study into 4 cohorts of about 25 participants each (expected retention 20
1644 per cohort). Each cohort will continue for ~7 months and will have the structure presented in
1645 Figure 5. Following recruitment, screening, and a run-in period of SAM, participants will be
1646 randomized into one of two groups: escalation vs. de-escalation of devices and function. Each
1647 treatment modality (SAM, PF, DSS) will continue for about 8 weeks, with the last 4 weeks used
1648 to assess GV from CGM data.

1649 **Escalation: SAM → PF → DSS**

1650 **De-escalation: DSS → PF → SAM**

1651 **14.2. Sample Size**

1652 **14.2.1. Sample Size Determination:**

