1690 intervention, and a minimum of 24 days of data is considered optimal for CGM-based CV
1691 determination.

1692 **14.3.2. Glucose Variability Reduction Achieved with CGM-based expert systems:**

1693 General linear models (GLM) (repeated measures ANOVA) will be used to assess the significance
1694 of the differences in average response between SAM, PF, and DSS across appropriate CGM-based
1695 metrics. The particular design of the clinical study allow for Aims 1.1, 1.2, and 1.3 to each be
1696 addressed independently in a randomized crossover analysis, as shown in Figure 4. While the
1697 randomized order of the interventions (escalation vs de-escalation) allows for an objective
1698 assessment of the average efficacy of each of them, we will introduce the order as a fixed factor
1699 to verify if significant study effects can be detected. Finally, we will study the evolution of GV
1700 within each modality period: GV and other CGM-based outcomes will be computed bi-weekly
1701 (the minimum length of time for precise GV assessment) and entered in a repeated measures

CLINICAL PROTOCOL

1702 GLM analysis; within-subject contrast (linear and polynomial) using 5 repeated measures per
1703 condition to explore the evolution of the glycemic outcomes in time; Aim 1.3.

1704 **14.4. Exploration of the effect of treatment escalation vs. de-escalation**

1705 A key advantage of the proposed study design (beyond the optimal statistical power) is the
1706 possibility to explore the glucose control and psycho-behavioral impact of features being added
1707 and/or enhanced with prescriptive components (DSS), vs. features being limited to information
1708 (PF) or even removed (SAM). We will perform this analysis by looking at the between factors in
1709 the repeated ANOVA analysis, contrasting the escalation group vs. de-escalation group. While
1710 not powered, this analysis will provide key insights in the future feature adaptation schemes
1711 based on the ATI.

1712 **14.5. Psychological and Behavioral Questionnaires**

1713 *Quantitative* data on usability and satisfaction will be analyzed using simple descriptive statistics.
1714 In addition, we will analyze scores from the measures in the psychosocial assessment battery to
1715 determine if changes occur over time and between groups. Using SPSS 26, we will construct
1716 predictive models in the general linear modeling (GLM) framework to examine each set of

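### The escalation versus de-escalation contrast is a between-person comparison with no baseline covariate, although every participant has SAM run-in CGM that could supply one.

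*Combined protocol and SAP*

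**What the plan says.** The same text stands in 1.3.3, 14.2.2 and 14.4. The method is given in one sentence: "We will perform this analysis by looking at the between factors in" "the repeated ANOVA analysis, contrasting the escalation group vs. de-escalation group. While" and the next sentence continues "not powered, this analysis will provide key insights in the future feature adaptation schemes". Section 14.3.2 adds, for the main model, "assessment of the average efficacy of each of them, we will introduce the order as a fixed factor". None of these places names a covariate. The only baseline covariates named for glycemic models are the psycho-behavioral traits of section 1.3.6 (Aim 2).

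Section 14.1 gives the two sequences as "Escalation: SAM → PF → DSS" and "De-escalation: DSS → PF → SAM". Sections 6.4 and 7.4 both state: "All participants in each randomization scheme use PF in Phase 2. Phase 2 initiation may be" carried out remotely or in clinic.

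On the run-in, section 5.2.1 says: "Participants will complete a minimum of 14 days (if CGM use within the preceding 3 months) or" 4 weeks otherwise. Section 5.3.1 uses the resulting data to check device use (11 of 14 days, or 22 of 28). The documents do not say that a run-in CV is calculated.

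**The concern.** In a repeated-measures ANOVA, the main effect of a between-subject factor compares the two groups' means over all phases. Person-to-person differences in CV do not cancel from that comparison as they do in the within-person comparisons of Aim 1. A pre-randomization measure of the same outcome is the natural covariate. It exists for everyone, and the plan does not use it.

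The average over three phases also shrinks any order effect that is not present in all of them. The plan presents this question as a main advantage of the design and intends the result to guide how later systems add or withdraw features. With a diluted, unadjusted contrast, a null result would say little about order or carryover, yet could be read as reassurance.

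**Working it through.** **The plan's own figure.** Section 14.2.1 gives an effect size of 0.22, α = 0.017, 95% power, correlation 0.55, 80 completers and 100 randomized. With the G*Power within-factor formula, λ = f²·N·m/(1−ρ), and f = 0.22, m = 2, N = 80: λ = 0.0484 × 160/0.45 = 17.2, power 95.4%. The smallest N for 95% is 79, and 80/(1−0.20) = 100. The figures reproduce if 0.22 is f; read as f², as printed, N would be 20. The plan gives no power figure for the order analysis.

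**Inputs.** From the plan: 80 completers, ρ = 0.55 between phases. Assumed: 40 per group (the allocation ratio is not stated), equal variances and equal correlations between phases, two-sided α = 0.05, and a run-in-to-phase correlation r. Units are SDs of one phase's CV.

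**Precision of the group contrast.**

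- Variance of a person's three-phase mean: (1 + 2ρ)/3 = (1 + 1.10)/3 = 0.70.
- After adjustment for run-in CV: 0.70 − r².

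| r | Adjusted variance | Reduction |
|---|---|---|
| 0.30 | 0.610 | 13% |
| 0.40 | 0.540 | 23% |
| 0.55 | 0.3975 | 43% |
| 0.65 | 0.2775 | 60% |

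The standard error of the group difference is √(2 × variance/40): 0.187 unadjusted and 0.141 at r = 0.55. The difference in three-phase means detectable with 80% power falls from 0.53 to 0.40 SD.

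**What the contrast measures.** It compares (SAM₁ + PF₂ + DSS₃)/3 with (DSS₁ + PF₂ + SAM₃)/3. Additive modality and period effects cancel. An effect δ in Phase 2 alone, or in Phase 3 alone, appears as δ/3; one equal in Phases 2 and 3 appears as 2δ/3.

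**The Phase 2 comparison.** Both groups are on PF in the same period. Its adjusted variance is 1 − r² = 1 − 0.3025 = 0.6975, standard error 0.187. For δ = 0.5 SD and r = 0.55:

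| Where the effect lies | Planned mean | Mean adjusted for run-in | Phase 2 adjusted for run-in |
|---|---|---|---|
| Phase 2 only | 14% | 22% | 75% |
| Phases 2 and 3 equally | 42% | 65% | 75% |
| Phase 3 only | 14% | 22% | no signal |

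Over r = 0.40 to 0.65, the 75% becomes 67% to 83%. Without adjustment, the Phase 2 comparison has 60% power. A 5,000-run simulation of the first row gave 14.5% for the planned mean and 74.4% for the adjusted Phase 2 comparison.

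**The case against.** The analysis is labelled exploratory and unpowered, and no aim rests on it. That stands, and it limits the weight of the point.

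The run-in correlation is not in the plan: the 0.55 of section 14.2.1 is for the repeated measures in the power calculation. A 14-day run-in with 11 days of use is short of the 24 days that 14.3.1 calls optimal, and under Chapter 4 the run-in can include stabilization after a switch from MDI to CSII. The correlation may well be below 0.55, so the range matters more than the 43%.

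Three stronger readings are tempting, and the documents support none of them.

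- *Phase 2 should replace the planned contrast.* Section 14.4 also asks about prescriptive features being added and about removal down to SAM. The steps from PF to DSS and from PF to SAM happen only at Phase 3, which a Phase 2 comparison cannot see.
- *Phase 1 is only noise.* De-escalation participants go from SAM run-in to DSS in one step at Phase 1, while escalation participants reach DSS through PF. Phase 1 also balances DSS against SAM in the group means; without it, Phase 3 would confound order with modality.
- *The modality-by-order interaction is useless because it is aliased with time.* This is true only of its SAM-versus-DSS component. The other component, PF minus the average of SAM and DSS, equals P₂ − (P₁ + P₃)/2 in both sequences (Pₖ is the CV in Phase k), so additive period effects cancel from the group comparison. Its variance is 1.5 × (1 − 0.55) = 0.675, slightly below 0.6975, and it needs no run-in data. The plan does not name it either, and it mixes in order effects from Phase 3.

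**Conclusion.** The point holds as a matter of efficiency and interpretation. The planned order contrast is between persons, names no baseline covariate, and leaves pre-randomization CGM unused. Adjusting for run-in CV would lower its variance by about 43% at r = 0.55, and by 13% to 60% over r = 0.30 to 0.65, given ρ = 0.55 between phases. The percentage does not depend on group size; the standard errors and power figures assume 40 per group.

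The dilution to one third or two thirds follows from averaging three phases. That reading rests on what a between-subject main effect tests, since the plan does not itself speak of an average. The powers of 14% and 75% describe the case most favourable to the Phase 2 comparison; in the least favourable case that comparison shows nothing.

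A reader might infer that the planned contrast is invalid or that Aim 1 is compromised. Neither follows: the contrast is free of additive modality and period effects, and Aim 1 rests on comparisons between modalities within participants.

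**What to change.** In 14.4, and in the matching text of 1.3.3 and 14.2.2:

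1. Keep the planned group contrast for CV and add run-in SAM CV as a covariate. State which run-in days define it, given that run-in length varies between participants.
2. Add, as a companion result, the Phase 2 CV on PF, escalation versus de-escalation, adjusted for run-in CV. State that it addresses arrival at PF from SAM or from DSS, and not changes made at Phase 3.
3. Optionally, name the interaction component that sets PF against the average of SAM and DSS as a further check.

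The cost is analysis wording and one derived variable from CGM already collected; no new visits or data are needed. The covariate concerns CV only; the psycho-behavioral part of 14.4 is not changed by it. The wording should be fixed before outcome data are examined, so that the choice among these contrasts is not made after seeing the results.

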476 experience. This will examine relevant core constructs of trust, acceptance, satisfaction,
477 confidence as well as fear, worries, distress and burden. Validated and reliable measures will be
478 used to explore psycho-behavioral characteristics and outcomes in addition to specifically
479 adapted measures for SAM and DSS technologies to capture holistic, disease-specific and
480 technology-specific data. These questionnaires will evaluate how specific constructs are
481 predictive of successful glycemic outcomes associated with DSS. These questionnaires will enable
482 us to assess important non-glycemic treatment outcomes that are meaningful to patients
483 including those affecting Quality of Life (QOL) (e.g. fear of hypoglycemia and diabetes distress).
484 To those ends, participants will complete a battery of questionnaires related to diabetes
485 management, treatment satisfaction and QOL at baseline (before system use) and after each
486 treatment modality.

487 **1.3.5. Ecological Momentary Assessment Data Collection**

488 Participants will be trained on the EMA surveys and requirements. During each treatment
489 condition, over the course of 2-3 days every two weeks, the participant will be asked to complete
490 a "Daily Diary" with 3-5 entries of 3-4 questions each day, for a minimum total of 48 entries per
491 participant during each Phase. The DiAs phone will display a text message containing a link to the
492 survey. Surveys will be triggered at fixed times, including a morning survey ~1h after waking up
493 and an end-of-the-day survey around 8-9 PM. Participants will be able to delay (up to 30 min) or
494 skip (up to 2 per day excluding at wake up) surveys for their convenience. Participants will
495 respond to questions on a 5-point Likert scale (0=Not at All, 4=Extremely). The first Diary for each
496 day will contain two additional items for rating sleep quantity/quality. The Daily Diary questions
497 are intended to assess agreement, trust, treatment satisfaction, diabetes burden, self-efficacy,
498 mood valence, energy level, physical well-being, and concerns about hypo- and hyperglycemia.
499 The first Diary for each day will contain two additional items for rating sleep quantity/quality.

CLINICAL PROTOCOL

500 **1.3.6. Mapping of Psycho-behavioral Characteristics to DSS Preferences and Performance**

501 Baseline assessments of psycho-behavioral traits will be introduced as covariates in the general

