670 evaluations are available, a decision will be made to determine the participant's eligibility for the
671 study or if one or more parts of the screening will have to be repeated. If at the first screening or
672 repeat screening an exclusionary condition is identified, the participant will be excluded from
673 participation with follow up and referred to their primary care physician as needed. The study
674 physician may elect to rescreen participants and collect additional laboratory values if their
675 clinical situation changes.

676 **3.5. Post-screening assessments**

677 If the subject is deemed eligible to participate in the study, the subject will elect to use either
678 continuous subcutaneous insulin infusion (CSII) or MDI therapy for the duration of the study, no
679 changes are allowed during the study. Furthermore, the participant will elect to use
680 carbohydrates counting or not for the computation of the meal bolus, this choice will apply to
681 the entire study.

682 Participants will then go through a baseline psycho-behavioral assessment. The following
683 questionnaires will be completed:

- 684 • Diabetes Specific Personality Questionnaire
- 685 • ABACUS
- 686 • Diabetes Locus of Control
- 687 • Confidence in Diabetes Self-Care Scale
- 688 • Clarke's Hypoglycemia Awareness Scale Participant Inclusion Criteria
- 689 • Demographic Data Survey (screening visit only)

690 **Chapter 4 Training Visit**

691 Participants may use CSII or multiple daily insulin (MDI) injection therapy for their diabetes
692 management. Participants will be asked to maintain this treatment throughout the study. In the
693 event that MDI participants elects to change to CSII therapy (see section 3.5), the run-in period
694 will include a period of insulin stabilization for up to 6 weeks. The study physician may elect to
695 extend this time frame if additional time would be beneficial to the participant.

696 If participants intend on identifying carbohydrate counting (carbohydrate ratio, insulin sensitivity
697 factor and glucose goal) at mealtime, they will be asked to continue to provide this information
698 throughout the study.

699 **4.1. Visit 2 - Study Equipment**

700 **4.1.1. Study Continuous Glucose Monitor Training**

701 A Dexcom G6 CGM will be provided to all participants at the training session. The participants
702 will be provided with CGM equipment and instructed to use the study CGM on a daily basis. If

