800 An appointment for Visit 3 will be scheduled.

801 **5.2.2. Questionnaires**

802 Participants will be sent the following questionnaires on the final week of the Run-in Period and
803 will be asked to complete them within 1 week:

- 804 • T1-Diabetes Distress Scale
- 805 • Hypoglycemia Fear Survey

CLINICAL PROTOCOL

- 806 • Hyperglycemia Avoidance Scale

807 **5.3. Visit 3 – Eligibility Assessment, Randomization and Training**

808 The participant may complete this visit via web conferencing and/or at the study site.

809 **5.3.1. Eligibility Assessment**

810 The CGM and insulin data will be reviewed to assess whether the subject has used the DiAs
811 system in SAM on at least 11 out of 14 days for CGM users or 22 out of 28 days for non-CGM
812 users. Subjects who are unable to meet the CGM and DiAs compliance requirement will be
813 withdrawn from the study, unless the investigator believes that there were extenuating
814 circumstances that prevented successful completion. In such cases, the investigator may ask the
815 participant to repeat this eligibility assessment.

816 **5.3.2. Adverse Event Assessment**

817 The participant will be asked about any of adverse events, adverse device effects, and device
818 issues since the last visit. The participant will also be asked if there were any low BGs <54 mg/dL,
819 high BGs >300 mg/dL, or ketones ≥ 3.0 mmol/L since the last visit. Participants will be encouraged
820 to contact the study team between visits as needed (i.e. report adverse events in real-time).

821 **Chapter 6 Study Procedures - Escalation**

822 **6.1.1. Randomization to Escalation**

823 Eligible subjects will be randomized to therapy escalation (SAM→PF→DSS).

824 A baseline Hemoglobin A1C will be collected. The participant will receive a mode change for
825 Phase 1 according to the randomization scheme.

826 **6.2. Sensor Augmented Mode**

827 Participants randomized to escalation will have any questions answered about continuing use of
828 the DiAs system in SAM.

829 **6.2.1. SAM EMA Surveys**

830 Over the course of 2-3 days every two weeks of Phase 2, the participant will be asked to complete
831 a “Daily Diary” with 3-5 entries of 3-4 questions each day, for a minimum total of 48 entries per
832 participant during each Phase.

833 **6.2.2. Phase 1 Initiation Questionnaires**

834 Participants randomized to escalation will complete the following questionnaires:

- 835 • Pittsburgh Sleep Quality Index

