1122 Participants randomized to de-escalation will complete the following questionnaires:

- 1123 • ABACUS

1124 **7.8.2. Adverse Event Assessment**

1125 The participant will be asked about any of adverse events, adverse device effects, and device
1126 issues since the last visit. The participant will also be asked if there were any low BGs <54 mg/dL,
1127 high BGs >300 mg/dL, or ketones ≥ 3.0 mmol/L since the last visit.

CLINICAL PROTOCOL

1128 **7.9. Post Study Check-In Visit (Visit 7)**

1129 Approximately 48 hours after the home use of the equipment, the study team will contact the
1130 participant via phone/email/text to assess:

- 1131 • Adverse events, adverse device effects, and device issues
1132 • Blood glucose values <60 mg/dL and >300 mg/dL

1133 **Chapter 8 Testing Procedures**

1134 **8.1. Laboratory / Point of Care Testing**

1135 **8.1.1. HbA1c**

- 1136 • A blood sample will be obtained at screening to obtain a baseline hemoglobin A1c level.
- 1137 • HbA1c level may be measured by study team using the DCA2000, a comparable point of
1138 care device, at time of screening
- 1139 • Labs may be obtained at a local laboratory (e.g. LabCorp) convenient to the participant.
- 1140 • Blood test may be obtained within 14 days prior to enrollment may be used for eligibility
1141 purposes.
- 1142 • Sample collected at randomization and end of study will be used for statistical purposes.

1143 **8.1.2. Comprehensive Metabolic Panel**

- 1144 • A blood sample will be obtained at screening to assess kidney and liver functioning.
- 1145 • Labs may be obtained at a local laboratory (e.g. LabCorp) convenient to the participant.
- 1146 • Blood test may be obtained within 14 days prior to enrollment may be used for eligibility
1147 purposes.

1148 **8.1.3. Thyroid Stimulating Hormone**

- 1149 • A blood sample will be obtained at screening to assess thyroid function.
- 1150 • Labs may be obtained at a local laboratory (e.g. LabCorp) convenient to the participant.
- 1151 • Blood test may be obtained within 14 days prior to enrollment may be used for eligibility
1152 purposes.

1153 **8.1.4. Pregnancy Test**

1154 A blood/urine pregnancy test will be required for women of childbearing potential at the
1155 screening visit, and between each phase . Tests must be negative to participate in the study.

1156 **Chapter 9 Questionnaires & Ecological Momentary Analysis**

1157 **9.1. Diabetes Specific Personality Questionnaire**

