1717 psychological factors (e.g., INSPIRE survey) over time, and their association with glycemic
1718 outcomes. Group assignment and Study Phases will be the primary covariate.

1719 **14.6. Baseline Descriptive Statistics**

1720 Baseline demographic and clinical characteristics of the cohort of all randomized participants will
1721 be summarized in a table using summary statistics appropriate to the distribution of each
1722 variable. Descriptive statistics will be displayed overall and by treatment group.

1723 Will include:

- 1724 • Age
- 1725 • HbA1c collected at randomization and study end
- 1726 • Gender
- 1727 • Race/ethnicity
- 1728 • CGM use before enrollment
- 1729 • Diabetes duration
- 1730 • BMI

1731 **14.7. Device Issues**

1732 We will count each time the participant interacted with the study Personalized Feedback and
1733 Decision Support System and perform a Wilcoxon paired rank test to determine if any differences
1734 exist in system interactions.

1735 **Chapter 15 Data Collection and Monitoring**

1736 **15.1. Case Report Forms and Device Data**

1737 The study data are collected through a combination of case report forms (electronic and paper)
1738 and electronic device data files obtained from the software and individual hardware
1739 components. These electronic device files and electronic CRFs are considered the primary source
1740 documentation.

1741 When data are directly collected in electronic case report forms, this will be considered the
1742 source data. Records will be maintained in accordance with ICH E6 and institutional regulatory
1743 requirements for the protection of confidentiality of participants.

1744 **15.2. Study Records Retention**

1745 Study documents will be retained for a minimum of 2 years after study close out. These
1746 documents may be retained for a longer period, however, if required by local regulations. No
1747 records will be destroyed without the consent of the Principal Investigator. It is the responsibility
1748 of the Principal Investigator to inform all co-investigators when these documents no longer need
1749 to be retained.

1750 **Chapter 16 Ethics/Protection of Human Participants**

1751 **16.1. Ethics Standard**

1752 The investigator will ensure that this study is conducted in full conformity with Regulations for
1753 the Protection of Human Participants of Research codified in 45 CFR Part 46, 21 CFR Part 50, 21
1754 CFR Part 56, and/or the ICH E6.

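### Section 14.5 gives the pre-intervention score no stated role when the groups are compared on a questionnaire, although seven scales have such a score in both groups

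*Combined protocol and SAP*

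**What the plan says.** Section 14.5 analyses the psychosocial battery to "determine if changes occur over time and between groups. Using SPSS 26, we will construct" general linear models. The models cover each set of "psychological factors (e.g., INSPIRE survey) over time, and their association with glycemic" outcomes, and the only statement on their terms is the one ending "outcomes. Group assignment and Study Phases will be the primary covariate".

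Section 1.3.4 has participants complete a battery covering "management, treatment satisfaction and QOL at baseline (before system use) and after each" modality. The schedule in 9.13 and the visit sections give these scores before Phase 1 in both groups:

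- Visit 1 (3.5, introduced by "Participants will then go through a baseline psycho-behavioral assessment. The following"): ABACUS, Diabetes Locus of Control, Confidence in Diabetes Self-Care.
- Last week of run-in (5.2.2, "Participants will be sent the following questionnaires on the final week of the Run-in Period and"): Diabetes Distress, Hypoglycemia Fear, Hyperglycemia Avoidance.
- Visit 3 (6.2.2 and 7.2.2): Pittsburgh Sleep Quality Index.

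Each of the seven is given again later. Section 1.3.6 does state a covariate role for starting scores: "Baseline assessments of psycho-behavioral traits will be introduced as covariates in the general" linear model. That model is for glycemic performance, not for questionnaire scores as outcomes.

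**The concern.** Fear, distress, confidence and numeracy differ between people in ways that persist. In a comparison between persons, those differences stay in the error term and in any chance imbalance between the groups unless the starting score is used. Section 14.5 leaves this open, so the analyst could ignore the score, treat it as one more level of time, or adjust for it. The three choices differ in precision.

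ABACUS is the plainest case. It is given only at Visit 1 and at exit (3.5, 6.8.1, 7.8.1). At exit the escalation group has just finished DSS and the de-escalation group has just finished SAM. No participant has an ABACUS score after any other phase, so no within-person contrast of modes exists.

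**Working it through.** **Inputs.** Section 14.2.1 gives 80 completers; I assume 40 per group, since the allocation ratio is not stated. That section's 0.55 is the correlation between repeated glucose CV measures, and I borrow it for questionnaires only as a midpoint. The 0.5 SD difference and two-sided 0.05 are my assumptions.

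**The plan's own figure.** No power is stated for any questionnaire. The CV sample size does reproduce if the printed effect size of 0.22 is taken as f: λ = f²·N·m/(1 − ρ) = 0.0484 × 80 × 2 / 0.45 = 17.2, giving 95.4% power at α = 0.017, and 80/0.8 = 100. This confirms how 80 and 0.55 were used, but says nothing about questionnaires.

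**Step 1: variance of one post-randomization score.** With unit SD before and after and correlation r:

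- unadjusted: 1
- change from baseline: 2(1 − r)
- adjusted for baseline: 1 − r²

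The adjusted variance is below the unadjusted by r² and below the change-score variance by 2(1 − r) − (1 − r²) = (1 − r)². It is therefore the smallest of the three for any r strictly between 0 and 1. At r = 0.55 the values are 1, 0.90 and 0.70.

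**Step 2: power.** Noncentral t with noncentrality (0.5/SD)·√(40/2) and 78 degrees of freedom, or 77 when adjusted. At r = 0.55 the noncentralities are 2.236, 2.357 and 2.677.

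| r | Unadjusted | Change | Adjusted | Gain over unadjusted | Gain over change |
|---|---|---|---|---|---|
| 0.30 | 59.8% | 46.3% | 63.9% | 4.0 | 17.6 |
| 0.50 | 59.8% | 59.8% | 72.2% | 12.4 | 12.4 |
| 0.55 | 59.8% | 64.4% | 75.3% | 15.5 | 10.9 |
| 0.70 | 59.8% | 81.4% | 87.1% | 27.3 | 5.8 |

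**Step 3: other differences, at r = 0.55.** At 0.2 SD the gain is 4.2 points over unadjusted and 3.1 over change; at 0.3 SD, 9.1 and 6.8; at 0.8 SD, 4.6 and 2.7.

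**Step 4: within-person contrasts.** For a difference between two phases, the share of variance removed by baseline is (r₁ − r₂)² / [2(1 − r₁₂)], where r₁ and r₂ are the correlations of baseline with each phase. It is zero when r₁ = r₂. Even with r₁ = 0.65, r₂ = 0.55 and r₁₂ = 0.55 it is 0.01/0.90 = 1.1%.

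**Step 5: which scales can be adjusted.**

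- INSPIRE and Technology Expectations are given before Phase 1 only in 7.2.2, under "Participants randomized to de-escalation will complete the following questionnaires"; the matching escalation list (6.2.2) contains only the Pittsburgh index.
- Technology Acceptance is given only after use.
- Locus of Control is repeated at Visits 5 and 6 in escalation (6.6.2, 6.8.1) but at Visits 4 and 5 in de-escalation (7.4.2, 7.6.2). Only Visit 5 is a shared administration.

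**The case against.** **Silence is not exclusion.** Calling group and phase primary does not make the list exclusive. Section 14.5 speaks of change over time, and 1.3.4 describes a series that begins at baseline. A reader might infer that the plan discards the starting score; the documents do not support that. ABACUS analysed over time can only run from Visit 1 to exit, so it must use the Visit 1 score, and the fair starting point there is the change score (64%, not 60%). This stands. The gap is that the role is unspecified, and for ABACUS the illustrative gain is about 11 points. It does not remove the point, because the change-score reading is still less efficient than adjustment.

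**The size is assumed.** A reader might infer a fixed cost in power. The documents give no SD, correlation, effect size or power target for any questionnaire, and 0.55 belongs to glucose CV. Only a range can be given.

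**The main mode comparisons are within person.** Distress, Hypoglycemia Fear, Hyperglycemia Avoidance, Confidence and Pittsburgh Sleep are repeated after every phase in both groups, so SAM, PF and DSS can be compared within participants, where baseline adds essentially nothing. This stands too. Averaging the three phases would show a larger gain (75% to 94% at r = 0.55 and 0.5 SD), but both sequences receive all three modes, so that average is a sequence effect. Section 14.4 calls the escalation versus de-escalation contrast unpowered and exploratory.

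**INSPIRE, the section's own example, cannot be adjusted.** Correct, and the fix must say so.

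**Conclusion.** The point holds as a gap in specification with a free improvement available. Section 14.5 compares groups on questionnaire scores and gives the same scale's starting score no stated role, although seven scales have one in both groups. For between-person comparisons, adjusting for it is at least as precise as either alternative at every correlation tried.

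Under the stated assumptions (40 per group, two-sided 0.05, 0.5 SD, equal variances before and after), the gain for a single post-randomization score over correlations 0.3 to 0.7 is about 4 to 27 points over no baseline and about 18 down to 6 over a change score. It is smaller at 0.2 or 0.8 SD.

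The within-person mode contrasts, including the primary CV comparison, are unaffected. These are secondary, largely exploratory analyses, so this is an improvement worth making and not a threat to the trial's main conclusion.

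**What to change.** Add to 14.5:

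- Each between-group comparison of a questionnaire score adjusts for the participant's own pre-Phase-1 score on that scale: Visit 1 for ABACUS, Locus of Control and Confidence; run-in for Distress, Hypoglycemia Fear and Hyperglycemia Avoidance; Visit 3 for Pittsburgh Sleep. Scores taken after Phase 1 begins serve only as outcomes. The Pittsburgh score is listed after the randomization step, so describe it as pre-Phase-1, not pre-randomization.
- ABACUS is analysed as exit score on group, adjusted for Visit 1 score.
- Locus of Control is compared at Visit 5 only, or matched by mode (after DSS: Visit 6 in escalation, Visit 4 in de-escalation; after PF: Visit 5 in both).
- INSPIRE, Technology Expectations and Technology Acceptance have no common pre-Phase-1 score and are not adjusted in this way.

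The cost is a short addition to the text and one degree of freedom per model. No new data or visits are needed.
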